Cover Letter:

Enclosed bellow documents are part of the Clinical Trial NCT03769649

Study Name: Clinical Evaluation of Safety and

Efficacy of The CelluTite Treatment

Revision Date: August 15, 2019

Clinical Evaluation of Safety an	l Efficacy of The C	ElluTite Treatment
----------------------------------	---------------------	--------------------

IRB ID: 7030

Rev. Date: August 15, 2019

Study Name: Clinical Evaluation of Safety and Efficacy of The

CelluTite Treatment

Protocol No.: DO608110

Revision No.: 4

Sponsor: InMode MD Ltd.

[name]

[name]

[name]

[name]

[contact]

[contact]

	Clinical Evaluation	on of Safety and Efficac	y of The CelluTite Treatment
	Protocol No:	DO608110C	Rev. Date: August 15, 2019
•	IRB ID:	7030	

Clinical Evaluation of	Safety	and Efficacy o	of The Cell	ˈuTite Treatment

IRB ID: 7030

Rev. Date: August 15, 2019

1. Protocol Synopsis

Study Title	Evaluation of Safety and Efficacy of The CelluTite Treatment
Protocol No	DO608110C
Sponsor	InMode MD Ltd.
Device	InMode RF system CelluTite RFAL hand piece HP172248.
	Morpheus8 Applicator
Study Design	Prospective single centre, open label clinical study.
Study Objectives	The aim of the study is to evaluate the safety and efficacy of cellulite treatment with HP172248 and Morpheus8.
Study Sites	[name], [name]
Patient Population and Sample Size	Approximately 10 female subjects , aged 18-70 having grade II and mild/moderate grade III cellulites.
Treatment areas	Exterior (lateral) and posterior thighs
	Optional: Buttocks with Morpheus Applicator only
Study Duration	Study duration for each subject is approximately seven months (including screening, one treatment and four follow-up visits at 1 week, 1 month, 3 months and 6 months post treatment.
	Overall study duration will be approximately 12 months, depending on the subject recruitment rate.
Efficacy Endpoints	Photographs evaluation: Photos from all time points (baseline and follow-up visits) will be evaluated by the treating physician and 2 blinded independent evaluators.
	Optional: Photos will be taken using QuantifiCare (imaging specializing in skin evaluations in clinical trials) at baseline and 6M FU visit.
	Evaluation goals are rating the degree of cellulite according to Clinician Reported Photonumeric Cellulite Severity Scale (CR-PCSS).

Clinical Evalua	tion of Safety and Eff	icacy of The CelluTite Treatment	
Protocol No:	DO608110C	Rev. Date: August 15, 2019	
IRB ID:	7030		

Safety Endpoint	Observation, assessment and recording of adverse events.		
	Evaluations will be done immediately after treatments and at all follow-up visit. The frequency, severity and causality of all adverse events will be recorded.		
	Possible treatment adverse effects include but are not limited by:		
	 Discomfort or pain Excessive skin redness (erythema) Excessive skin swelling (edema) Bruising Damage to natural skin texture (crust, blister, burn) 		
	- Change of pigmentation (hyper- and hypo-pigmentation)		
	- Scarring - Excessive Bleeding		
	- Surface Irregularity		
	- Numbness		
	- Seroma		
	- Severe and persistent reactions are reportable as adverse events.		
	Each subject will undergo at least 5 study visits including screening, 1 treatment and 4 follow-up visits.		
	Visit 1: - Screening will be performed to determine subject eligibility as well as to collect all of the required medical information and obtain signed Informed Consent.		
	 Baseline photos will be performed. Treatment may occur on the same day of screening or within 3 weeks following screening. 		
	Visit 2: Follow-up visit – 1 week following treatment. Safety follow-up to insure that patient recovery is proper. Photos and assessments will be performed.		
	Visit 3: Follow-up visit – 1 month following treatment. Photos and assessments will be performed.		
	Visit 4: Follow-up visit – 3 months following treatment. Photos and assessments will be performed.		
	Visit 5: Follow-up visit – 6 months following treatment. Photos and assessments will be performed.		
	- After the treatment and at all visits, adverse events will be recorded.		
	- Duration of the screening and treatment visit is approximatly 2-3 hours and the		
Main Eligibility	follow-up visit is approximatly 1 hour. Inclusion Criteria		
Criteria	- Female subjects aged 18-70 having mild/moderate grade cellulites.		

Clinical Evaluatio	n of Safety and Efficac	y of The CelluTite Treatment
Protocol No:	DO608110C	Rev. Date: August 15, 2019
IRB ID:	7030	

- The patients should understand the information provided about the treatment, possible benefits and side effects, and sign the Informed Consent Form, (including the permission to use photography).
- The patients should be willing to comply with the study procedure and schedule, including the follow up visit, and will refrain from using any other aesthetic treatment methods in the treatment area for the last 6 months and during the entire study period.

Exclusion Criteria:

- Body fat layer thinner than 5mm.
- Pacemaker or internal defibrillator, or any other active electrical implant anywhere in the body.
- Superficial permanent implant in the treated area such as metal plates and screws, metal piercing, silicone implants or an injected chemical substance.
- Current or history of skin cancer (remission of 5 years), or current condition of any other type of cancer, or pre-malignant moles.
- Severe concurrent conditions, such as cardiac disorders, epilepsy, uncontrolled hypertension, and liver or kidney diseases.
- Pregnancy and nursing.
- History of bleeding coagulopathies or use of anticoagulants.
- Impaired immune system due to immunosuppressive diseases such as AIDS and HIV or use of immunosuppressive medications.
- Poorly controlled endocrine disorders, such as diabetes or thyroid dysfunction and hormonal virilization.
- Any active condition in the treatment area, such as sores, psoriasis, eczema, and rash.
- History of skin disorders, keloids, abnormal wound healing, as well as very dry and fragile skin.
- Use of Isotretinoin (Accutane®) within 6 months prior to treatment.
- Any surgery or treatment such as laser or chemicals in treated area within 3-6 months prior to treatment or before complete healing.
- Allergies, in particular to anesthesia.
- Mental disorders such as Body Dysmorphic Disorder (BDD).
- As per the practitioner's discretion, refrain from treating any condition that might make it unsafe for the patient.

Clinical Evaluation of Safety and Efficacy of The CelluTite Treatme	Clinical Evalud	ation of Saf	etv and Efficacv	of The CelluTite	Treatmer
---	-----------------	--------------	------------------	------------------	----------

IRB ID: 7030

Rev. Date: August 15, 2019

TABLE OF CONTENTS

1.	P	ROTOCOL SYNOPSIS	4
2.	IN	NTRODUCTION & STUDY RATIONALE	10
3.	D	EFINITIONS, ACRONYMS AND ABBREVIATIONS	10
4.	D	EVICE DESCRIPTION	11
5.	S	TUDY OBJECTIVES	12
6.	S	TUDY ENDPOINTS	12
6	5.1	Efficacy Endpoints	12
6	5.2	Safety Endpoint	15
7.	S	TUDY POPULATION	16
7	'.1	General Considerations	16
7	.2	Inclusion Criteria	17
7	'.3	Exclusion criteria	17
8.	S	TUDY DESIGN	17
8	3.1	Screening and Baseline (Visit 1)	18
8	3.2	Treatment	18

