7.1 General Considerations

The study will recruit approximately 70 female subjects, between the ages of 18-70, having small body areas with adipose tissue, seeking cellulite treatments.

Treatment areas include Exterior (Lateral) and posterior thighs

Optional: Buttocks treated with Morpheus Applicator only

Eligible subjects will be screened. Investigators will screen subjects based on the inclusion/exclusion criteria described below after a written informed consent is signed.

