7.3 Exclusion criteria

- Body fat layer thinner than 5mm.
- Pacemaker or internal defibrillator, or any other active electrical implant anywhere in the body.
- Superficial permanent implant in the treated area such as metal plates and screws, metal piercing, silicone implants or an injected chemical substance.
- Current or history of skin cancer (remission of 5 years), or current condition of any other type of cancer, or pre-malignant moles.
- Severe concurrent conditions, such as cardiac disorders, epilepsy, uncontrolled hypertension, and liver or kidney diseases.
- Pregnancy and nursing.
- History of bleeding coagulopathies or use of anticoagulants.
- Impaired immune system due to immunosuppressive diseases such as AIDS and HIV or use of immunosuppressive medications.
- Poorly controlled endocrine disorders, such as diabetes or thyroid dysfunction and hormonal virilization.
- Any active condition in the treatment area, such as sores, psoriasis, eczema, and rash.
- History of skin disorders, keloids, abnormal wound healing, as well as very dry and fragile skin.
- Use of Isotretinoin (Accutane®) within 6 months prior to treatment.
- Any surgery or treatment such as laser or chemicals in treated area within 3-6 months prior to treatment or before complete healing.
- Allergies, in particular to anesthesia.
- Mental disorders such as Body Dysmorphic Disorder (BDD).
- As per the practitioner's discretion, refrain from treating any condition that might make it unsafe for the patient.

8. Study Design

The study is a prospective, open label clinical study.

Approximately 70 subjects will be recruited for the study.

Clinical Evaluation of Safety and Efficacy of The CelluTite Treatment		
Protocol No:	DO608110C	Rev. Date: August 15, 2019
IRB ID:	7030	

Treatment areas include Exterior (Lateral) and posterior thighs

Optional: Buttocks treated with Morpheus Applicator only

The treatment will be conducted according to the guidelines in the operator manual.

The treatment efficacy will be evaluated by comparing 1, 3 and 6 months follow-up photos and cellulite grade to baseline.

Each subject will undergo 5-6 study visits including screening, treatment and 4 follow-up visits.

The Time and Events Schedule is provided in Appendix I.

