9.1 Efficacy Measures

The below assessments will be conducted at baseline and follow-up visits.

Photos from all time points (baseline before treatment and at follow-up visits) will be evaluated by the treating physician and 2 blinded independent evaluators.

[figure not shown]
Evaluation goals are rating the degree of cellulite.

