14.1 Documentation List

Accurate, complete and timely documentation is essential to the successful conduct of this study. The following documents will be created and maintained:

- 1. Informed Consent Forms (ICFs).
- 2. Case Report Forms (CRFs).
- 3. Adverse effect reports to sponsor.
- 4. Adverse effect reports to IRB.
- 5. Inventory Log.
- 6. Monitoring logs.
- 7. IRB approval for protocol.
- 8. IRB approval for informed Consent.
- 9. Final report to Sponsor and IRB.
- 10. Records of protocol deviations.
- 11. Record of protocol amendments.
- 12. 1 copy of each protocol revisions.
- 13. 1 copy of each CRF revision.
- 14. Clinical Trial Agreement.
- 15. All correspondence relating to study.

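### The planned sample size is about 10 in the synopsis but about 70 in Sections 7.1 and 8, and nothing in the text says which governs

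*Combined protocol and SAP*

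**What the plan says.** The recruitment target appears in three places:

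- **Section 1 (Synopsis), row on patient population and sample size:** "Approximately 10 female subjects".
- **Section 7.1 (General Considerations):** "The study will recruit approximately 70 female subjects, between the ages of 18-70".
- **Section 8 (Study Design), opening lines:** "Approximately 70 subjects will be recruited for the study".

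The synopsis describes the design as "Prospective single centre, open label clinical study". On timing it says "Study duration for each subject is approximately seven months" and "Overall study duration will be approximately 12 months, depending on the subject recruitment rate".

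Section 16 defines a safety set of all treated subjects, a performance set of those with at least one post-treatment measurement, and a paired t-test at a two-tailed level of 0.05. It gives no sample size, power, effect size, standard deviation or dropout allowance.

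**The concern.** The word approximately can absorb a few subjects either way. It cannot absorb a factor of seven. The protocol therefore carries two enrolment targets, and a site could stop near 10 or continue to about 70 and claim compliance either way. A monitor checking adherence has no single number to check against.

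Three things are left open: when recruitment ends, how many people have incisions, tumescent anaesthesia and cannula insertion, and how precise the efficacy and safety results will be. The number exposed to the procedure is the most serious of these.

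A lesser point is that two targets leave the end of an open-label study to be chosen while results accumulate. The plan limits this risk. Photographs "will be evaluated by the treating physician and 2 blinded independent evaluators", and no interim look is planned. If enrolment closes at about month 5, no 6-month result would yet exist, although some 1-month and 3-month results would.

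**Working it through.** **1. Can either figure be reproduced?** No. Section 16 gives only the test and its level, so neither 10 nor 70 can be derived from the plan.

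**2. Can the figures be reconciled?** Each harmless reading was checked against the text:

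| Reading | What the text shows |
|---|---|
| 10 per site, 70 in total | The synopsis says single centre; no per-site number appears |
| 10 as a pilot or first stage | No stage or cohort is described |
| One figure screened, the other treated | Sections 7.1 and 8 both speak of recruitment; the synopsis gives its figure as the sample size |
| Body overrides synopsis, or the reverse | No precedence statement |
| One figure is superseded text in a change log | No change log in the text; all three places are current |

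Two mentions of 70 against one of 10 do not settle it, because either figure could be the one left out of date.

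**3. Size of the gap.** 70 − 10 = 60 subjects; 70 / 10 = 7.

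**4. Consequence for efficacy (illustration).** From Section 16.2: paired t-test, two-sided 0.05. Assumed, because the plan does not say: one score per subject, all subjects evaluable, and 80% power for the detectable change. Results are in SDs of the change, since no SD is stated.

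- Half-width of the 95% confidence interval = t(0.975, n−1) / √n. n = 10: **0.715 SD**. n = 70: **0.238 SD**. Ratio 0.7154 / 0.2384 = 3.0.
- Detectable change d solves 1 − F(t(0.975, n−1); n−1, d√n) = 0.80, where F is the noncentral t distribution function (the opposite tail is negligible). n = 10: **0.996 SD**. n = 70: **0.340 SD**.

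**5. Consequence for safety (illustration).** The denominator is the Section 16.1 safety set. The one-sided 95% bound is a choice made here. With zero events, upper bound = 1 − 0.05^(1/n).

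- n = 10: 1 − 0.05^(1/10) = **25.9%**
- n = 70: 1 − 0.05^(1/70) = **4.2%**

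For an adverse event with an assumed true rate of 5%, the chance of seeing at least one case is 1 − 0.95^n: 40% at n = 10 and 97% at n = 70.

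**6. Does the timeline show which target was meant?** Even enrolment is assumed.

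| Enrolment window | 10 subjects | 70 subjects |
|---|---|---|
| 12 − 7 = 5 months | 10 / 5 = 2.0 per month | 70 / 5 = 14.0 per month |
| 12 − 6 = 6 months (subtracting only the 6-month follow-up) | 1.7 per month | 11.7 per month |

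No recruitment rate is stated, and the synopsis makes the 12 months depend on that rate. The timeline cannot decide between the two.

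**The case against.** The strongest objection is that the whole point turns on one digit in one table cell of machine-read text. Other parts of the same text are visibly garbled, including the title line, some section numbers in the contents list and the relationship-to-device table in Section 12.1. A 7 misread as a 1 would produce exactly this conflict, and a reading error is not an error in the plan. This stands as a caution. The rest of the cell, including its age range ending in 70, reads cleanly, so a misread is possible but not shown. It is a reason to look at the page first.

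Two limits on scope also stand. Some pages are absent from the text and the site entry is masked, so the claim can only be that nothing in the text supplied reconciles the figures. The single-centre statement comes from the synopsis alone, and Section 14.5 mentions principal investigators in the plural. That does not establish a per-site target, but the monthly rates above should not be read as firmly single-site figures.

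Finally, the planned analysis runs unchanged at either size and the protocol makes no power claim, so nothing in Section 16 is broken. That is correct. The precision and safety figures show what depends on the answer; the finding itself rests on the conflicting targets.

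**Conclusion.** The concern holds. As the text reads, one revision gives two recruitment targets, about 10 once and about 70 twice, and the governing number cannot be determined from it. At least one place is wrong. The discrepancy is 60 subjects, which would separate the two targets by a threefold difference in interval width and about a sixfold difference in the zero-event bound (25.9 / 4.2 = 6.2), under the assumptions given in the working.

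It must be fixed because it determines how many people receive an invasive procedure. The one condition is that the synopsis cell really reads 10. If the page image shows 70, the point falls away.

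**What to change.** 1. Check the digit in the synopsis cell against the page image.
2. If it reads 10, the sponsor confirms the intended, IRB-approved number from the IRB approval and the "Record of protocol amendments" that Section 14.1 requires to be kept. Neither 10 nor 70 should be assumed.
3. State that one number in the synopsis and in Sections 7.1 and 8, for example: *Approximately [confirmed N] female subjects will be recruited.*
4. Check that the overall duration of about 12 months is workable for the confirmed number.

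**Cost.** A short amendment: one place changes if 70 is confirmed, two if 10 is confirmed, three if it is neither. Section 13.4 sends protocol changes to the IRB, and Section 14.3 requires approval before implementation where the amendment is significant. If 10 is confirmed, the study's precision will look less favourable. If 70 is confirmed, the 12-month duration may need revising. Adopting 70 without confirmation could expose about 60 more people to the procedure than was intended.

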6.2 Safety Endpoint

Observation, assessment and recording of adverse events. Evaluations will be done immediately after treatment and at all follow-up visits. The frequency, severity and causality of all adverse events will be recorded.

Possible CelluTite adverse effects include but are not limited by:

- Discomfort or pain
- Excessive skin redness (erythema)

- Excessive skin swelling (edema)
- Ecchymosis
- Damage to natural skin texture (crust, blister, burn)
- Change of pigmentation (hyper- and hypo-pigmentation)
- Scarring
- Very slight risk of infection
- Incision port scarring
- Surface Irregularity
- Numbness
- Seroma
- Side effects related to anesthesia

Possible Morpheus8 adverse effects include but are not limited by:

- Discomfort or pain
- Excessive skin redness (erythema)
- Excessive skin swelling (edema)
- Damage to natural skin texture (crust, blister, burn)
- Change of pigmentation (hyper- and hypo-pigmentation)
- Localized infection
- Scarring

Erythema lasting not longer than 24h and edema for 1-3 weeks is a typical skin reaction to the Morpheus8 treatment.

Crusting from the ablated dots will exfoliate naturally after 1-3 weeks.

Adverse events will be classified as Mild, Moderate, and Severe. The duration of the adverse event until it subsides will also be recorded.

7. Study Population

[figure not shown]

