12.1 Definitions

Adverse Event:

An Adverse Event (AE) is any untoward medical occurrence (sign, symptom, illness, abnormal laboratory value, or other medical event) in a subject. This definition does not imply that there is a relationship between the adverse event and the device. (Significant device failure may constitute an adverse event if an undesirable experience occurs).

An Adverse Device Effect (ADE) is any untoward and unanticipated response to a medical device. This definition includes any event resulting from insufficiencies or inadequacies in the instructions for use or the deployment of the device, or any event that is a result of a user error.

Serious Adverse Event (SAE):

A serious adverse event (SAE) is any adverse event that:

- Led to death
- Led to a serious deterioration in the health of the subject that resulted in a lifethreatening illness or injury
- Resulted in a permanent impairment of a body structure or a body function
- Required in-subject hospitalization or prolongation of existing hospitalization
- Resulted in medical or surgical intervention to prevent permanent impairment to body structure or a body function
- Led to fatal distress, a congenital abnormality, birth defect or death

Unanticipated Adverse Event:

An unanticipated adverse event is any serious, device-related adverse event, if that event was not previously identified in the risk analysis and Informed Consent form in nature, severity, or frequency.

AE Severity:

[figure not shown]
Adverse events are graded according to severity as follows:

Mild	Sign or symptom, usually transient, requiring no special treatment and	
	generally not interfering with usual activities.	
Moderate	Sign or symptom, which may be ameliorated by simple therapeutic	
	measures; yet, may interfere with usual activity.	
Severe	Sign or symptom that are intense or debilitating and that interfere w	
	usual activities. Recovery is usually aided by therapeutic measures.	

Relationship to Device:

The relationship of the adverse event to the treatments or procedures is defined as follows:

Most Probably Related	Follows a reasonable temporal sequence from study device
iviost Frobably Related	delivery/retrieval and cannot be reasonably explained by known

	characteristics of the subject's clinical data or the surgical procedure applied.		
	Follows a reasonable temporal sequence from study device		

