12.4 Investigator Records

The Investigator will report all Adverse Events which occur with each subject throughout the study and follow-up period and will record them in the CRF Adverse Events Investigation Form. The Investigator will categorize Adverse Events according to:

- Serious or non-serious
- Severity
- Anticipated or unanticipated
- Relationship to device use

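### One synopsis line sets a severe-and-persistent threshold for adverse events that conflicts with the record-all rule elsewhere, and the plan does not say whether expected reactions such as crusting are counted

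*Combined protocol and SAP*

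**What the plan says.** **Synopsis, Safety Endpoint.** The cell first states "The frequency, severity and causality of all adverse events will be recorded". It then lists possible effects and closes the list with "Severe and persistent reactions are reportable as adverse events". Neither the synopsis nor any later section says how long a reaction must last to be persistent.

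**Sections 6.2 and 9.2.** Both repeat the rule that all AEs are recorded, without the threshold. Both add "Adverse events will be classified as Mild, Moderate, and Severe" and require the duration of each AE to be recorded.

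**Section 12.1.** "An Adverse Event (AE) is any untoward medical occurrence". Its lowest severity grade covers signs that are usually transient and need no special treatment.

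**Sections 12.4, 12.5 and 14.2.** Section 12.4 says "The Investigator will report all Adverse Events which occur with each subject throughout the study and follow-up period" and has each event categorised by seriousness, severity, anticipated or unanticipated, and relationship to the device. Section 12.5 sends even the AEs not covered by its faster routes to the sponsor within 5 working days. Section 14.2 provides a form for all AEs.

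**Expected reactions.** Sections 6.2, 9.2, 11.1 and 12.2 each list "Damage to natural skin texture (crust, blister, burn" among the possible adverse effects. For Morpheus8 they then say "Erythema lasting not longer than 24h and edema for 1-3 weeks is a typical skin reaction to the Morpheus8 treatment" and, in the next sentence, "Crusting from the ablated dots will exfoliate naturally after 1-3 weeks". Erythema and edema appear in the lists of effects only when excessive, and no cut-off is given.

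**The concern.** Safety is half of the study objective, and AE recording is its only endpoint. The study is open label, and no control group is described that would show whether events had been classified differently from what was intended. If the synopsis line is read as the threshold for what becomes an AE, part of the safety record is lost at the point of entry, and events that were never written down cannot be recovered at analysis.

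Removing that line does not settle everything. A subject with ordinary Morpheus8 crusts at the 1-week visit matches an entry in the list of adverse effects and also matches the description of the normal course. The same holds for short-lived erythema and for edema within 1-3 weeks, where the word excessive decides the matter and is not defined. One investigator might log all of these and another none, and both could point to the protocol.

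**Working it through.** The plan states no expected AE rate, safety threshold or safety sample-size calculation, so there is no figure to reproduce. The check is a comparison of the counting rules, followed by a bound.

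**Step 1. What each rule captures.**

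| Event | Synopsis threshold line | Synopsis record-all sentence; 6.2, 9.2, 12.1, 12.4, 12.5, 14.2 |
|---|---|---|
| Mild AE | not captured | captured |
| Moderate AE | not captured | captured |
| Severe, transient AE | not captured (both conditions are required) | captured |
| Severe, persistent AE | captured | captured |

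The first column takes the line as a threshold. On that reading the two columns agree only in the last row. The conflict lies inside the synopsis cell as well as between the synopsis and the body.

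**Step 2. Does the word reportable reconcile them?** If the line concerned only reporting to the sponsor, recording could still be complete. Section 12.5 rules this out, because it also requires all remaining AEs to be reported in writing. No section says whether the synopsis or section 12 takes precedence.

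**Step 3. Expected reactions.** Section 12.2 is headed as a list of anticipated adverse events and contains both the crust entry and the sentence on its natural course. With the anticipated/unanticipated category in section 12.4, ordinary crusting can be recorded as an anticipated AE. That shows the plan has a place for it. It does not show that sites must put it there, and no section says so.

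**Step 4. Timing.** AEs are assessed right after treatment and at 1 week, 1 month, 3 months and 6 months. The 24 h and 3-week marks fall between visits. Sections 6.2 and 9.2 require duration to be recorded, which can be done by asking the subject, but they require it for AEs. A reaction not classed as an AE would not be covered.

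**Step 5. Bound on the effect.** Let p be the share of subjects whose only reactions are mild or transient, and assume that no subject has a severe and persistent one. The proportion of subjects with an AE is then 0 under the threshold line and p under the record-all rule. The documents give no p, so it is taken from 0% to 100%.

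Exact (Clopper-Pearson) 95% intervals are given at the two sample sizes that the protocol states, about 10 in the synopsis and about 70 in sections 7.1 and 8. That discrepancy is a separate matter. For 0 of n the upper limit is 1 − 0.025^(1/n); for n of n the lower limit is 0.025^(1/n).

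| Rule | Assumed p | n = 70 | n = 10 |
|---|---|---|---|
| Threshold line | any | 0/70: 0-5.1% | 0/10: 0-30.8% |
| Record all | 50% | 35/70: 37.8-62.2% | 5/10: 18.7-81.3% |
| Record all | 100% | 70/70: 94.9-100% | 10/10: 69.2-100% |

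These rows show what the choice of rule could do to the same patients. They do not predict what will be seen.

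**The case against.** The strongest reply is that the plan has one operational rule and one badly worded line. The synopsis line does not contain the word only. The cell that holds it also requires all AEs to be recorded, and the synopsis visit text requires AEs to be recorded after treatment and at every visit. Every later section agrees. Ordinary crusting fits the anticipated category, duration is already to be recorded, and no safety test depends on the count.

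Most of this stands, and it limits what can be concluded. A reader might infer the following, which the documents do not support:

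- **That the synopsis counts only severe and persistent reactions.** This is an inference from one sentence, and the same cell contradicts it.
- **That the documents leave AE frequency wholly undetermined.** Sections 12.1 and 12.4 give a usable rule. The problem is that another line conflicts with it.
- **That crusting is called a typical reaction.** That phrase is attached to erythema and edema; crusting is described in the next sentence.
- **That frequency is the only safety measure.** Severity, causality and duration are recorded too.
- **That durations cannot be known because of the visit schedule.** Duration is to be recorded for AEs, and the case report form is not among the documents, so missing date fields cannot be asserted.

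The reply does not remove the conflict. The threshold sentence is in the protocol, and if it sets no threshold it has no evident function. The anticipated category helps only once a reaction has been entered as an AE.

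**Conclusion.** The point holds as an internal contradiction plus an unstated rule. The synopsis line conflicts with its own cell and with sections 6.2, 9.2, 12.1, 12.4, 12.5 and 14.2. A site that followed it would omit mild, moderate and severe-but-transient events. Separately, no section says whether ordinary crusting, or erythema and edema of the kind called typical, is counted as an AE.

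The size of the effect is unknown. The 0% to 100% range rests on two assumptions: that no reaction is both severe and persistent, and that p may take any value. It is the widest possible range and should not be read as an expected distortion. Nor do the documents show that any site would follow the synopsis line. They show that it could, and that the reported frequency could then differ with identical clinical findings. The correction is specific and cheap, and it should be made because events left off the form cannot be restored later.

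**What to change.** 1. Delete the threshold sentence from the synopsis, or align it with section 12.1. Apply the 12.1 definition and the 12.4 record-all rule throughout.
2. State in sections 6.2, 9.2 and 12.2 that every local reaction, including expected ones, is recorded as an AE with severity, start date, stop date and the existing anticipated/unanticipated category. The dates serve the duration requirement already in 6.2 and 9.2.
3. Add an AE summary to section 16.2, which has none. On the safety analysis set, tabulate anticipated reactions separately from other AEs, alongside the total.
4. Do not use 24 h or 1-3 weeks as a cut-off for leaving events out. The protocol gives these as descriptions of Morpheus8 reactions, never as AE limits, and gives none for CelluTite, although the thighs receive both. Using them as cut-offs would also contradict section 12.1, which has no duration threshold.

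The cost is protocol wording, a small amount of extra recording, and a total AE rate that may look less favourable. The separate table lets a reader see how much of that total is anticipated. Treatment and visits do not change.
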